#### 6.6.1.3 Study Drug Dose Modifications

##### **DOSE REDUCTIONS**

Dose reduction refers to a situation where a dose level was reduced from the previous dose level without going back. Dose reduction could apply to any of the study drugs.

##### **DOSE INTERRUPTIONS**

Dose interruption refers to a situation where a subject had a planned temporary break from taking the study drug for a short period (ie, interruption period). Dose interruptions will only be determined for lenvatinib.

Dose interruption only refers to the scenario where the dose levels or dosing frequencies before and after interruption period (defined as the period with dose=0) are the same. For example: 14 mg/m^2 lenvatinib followed by 0 mg and followed by 14 mg/m^2 lenvatinib. If

the dose level after dose interruption period was reduced from the dose level before the interruption period, it should be counted as dose reduction and should not be counted as dose interruption. An example of dose reduction instead of dose interruption:

- 14 mg/m^2 lenvatinib followed by 0 mg followed by 11.2 mg/m^2 lenvatinib.

Please note, for the scenario above, the period with dose=0 should be counted as dose reduction period and not dose interruption (ie, the dose reduction date should be the date of dose=0). If the subject discontinued from treatment permanently after dose interruption with dose=0, it should be counted as treatment discontinuation instead of dose interruption.

The number of subjects with dose reductions for each individual study drug and with dose interruptions for lenvatinib will be summarized. The number (ie, frequency) of dose reductions per subject will also be summarized.

Time to first dose reduction is defined as the time period from the first dose date to the date of first dose reduction, or the time period from the first dose date to the date of first dose interruption for those subjects who had dose interruption first and then followed by dose reduction. Time to first dose reduction will be derived and summarized descriptively for lenvatinib for those subjects who had at least one dose reduction during the treatment period.

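### SAP 6.6.1.3: as worded, the second branch of time to first dose reduction dates a lenvatinib reduction at an earlier same-dose interruption, in conflict with the SAP's own definitions

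*SAP*

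**What the plan says.** All the relevant text is in SAP Section 6.6.1.3, under Dose Reductions and Dose Interruptions.

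- **Reduction.** The dose level is lowered from the previous level and does not go back.
- **Interruption.** "Dose interruption only refers to the scenario where the dose levels or dosing frequencies before and after interruption period" are the same. The example is 14 mg/m² "followed by 0 mg and followed by 14 mg/m 2 lenvatinib".
- **Zero-dose period ending at a lower dose.** The example is 14 to 0 to 11.2 mg/m². Here "it should be counted as dose reduction and should not be counted as dose interruption", and "the dose reduction date should be the date of dose=0".
- **Time to first dose reduction, branch 1.** "Time to first dose reduction is defined as the time period from the first dose date to the date of first dose reduction".
- **Time to first dose reduction, branch 2.** The interval ends instead at "the date of first dose interruption for those subjects who had dose interruption first and then followed by dose reduction".

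The variable is summarized descriptively, for lenvatinib only, in subjects with at least one reduction. Section 6 sets the day count for durations as end date minus start date plus 1.

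**The concern.** By the SAP's own classification, a hold that leads straight to a lower dose is a reduction, and its date is already the first day of zero dose. Branch 1 handles it. Branch 2 is then left with subjects who stopped, resumed at the same dose and were reduced at some later time. For them it replaces the date of the reduction with the date of the earlier interruption. The text sets no maximum gap and does not require the two events to be adjacent or to share a cause.

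What is at stake is a tolerability summary for the investigational drug. If branch 2 is programmed literally, a variable labelled as time to first reduction becomes, for some subjects, time to first interruption. Any error goes one way, towards earlier reduction. Two programmers working from the same text could also derive different values.

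**Working it through.** The SAP states no figure on this point, so there is none to reproduce. The check applies the definitions to dosing histories.

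**Inputs from the SAP.** The dose levels 14, 0 and 11.2 mg/m² and the classification and dating rules come from Section 6.6.1.3. The day count comes from Section 6.

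**Assumed inputs.** All calendar days are hypothetical, with the first dose on Day 1. The SAP contains no dosing data.

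**Rules applied**

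1. Zero dose, then the same level as before: interruption, dated at the start of zero dose.
2. Zero dose, then a lower level: reduction, dated at the start of zero dose.
3. A lower level with no zero-dose period: reduction, dated on the day of the lower dose.
4. Own-date value = (date of first reduction − 1) + 1.
5. Literal value = (date of first interruption − 1) + 1 if an interruption precedes the first reduction; otherwise the own-date value.

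**Results**

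| History (mg/m²) | Own-date value (days) | Literal value (days) | Shift (days) |
|---|---|---|---|
| A: 14 → 0 (Day 20) → 11.2 (Day 27) | 20 | 20 | 0 |
| B: 14 → 0 (Day 20) → 14 (Day 27) → 11.2 (Day 41) | 41 | 20 | 41 − 20 = 21 |
| C: 14 → 0 (Day 20) → 14 (Day 27) → 11.2 (Day 110) | 110 | 20 | 110 − 20 = 90 |
| D: 14 → 0 (Day 20) → 14 (Day 27) → 0 (Day 110) → 11.2 (Day 117) | 110 | 20 | 110 − 20 = 90 |
| E: 14 → 11.2 (Day 110), no zero dose | 110 | 110 | 0 |

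In A, the case the SAP itself illustrates, branch 2 adds nothing: the reduction is already dated at Day 20. In E there is no interruption. The branch changes the value only in B, C and D, where a same-dose interruption comes before the first reduction.

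History D shows the conflict most directly. The dating rule puts the reduction at Day 110, the start of the zero-dose period that ends at 11.2 mg/m². Branch 2 puts it at Day 20, the start of a period after which the subject returned to 14 mg/m². Under the SAP's definition of a reduction, no reduction had occurred at Day 20.

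**The case against.** The strongest objection is that Section 6.6.1.3 does not keep to its strict definition. It speaks of the case where "the dose level after dose interruption period was reduced from the dose level before the interruption period", and of a subject who "discontinued from treatment permanently after dose interruption with dose=0". Neither period is an interruption in the strict sense, so the author also uses the term for any zero-dose period. The wording of branch 2 also resembles the 14 to 0 to 11.2 example. On that view the branch only restates the dating rule. If it is confined to the zero-dose period directly before the reduction, all five histories receive the reduction's own date and there is no bias.

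This stands in part. The direct sequence may well be what was meant, so a misreported summary is possible but not certain. It does not remove the problem. A looser term adds other zero-dose periods to the category but still includes same-dose holds, which are its defined meaning. The clause also points to the first interruption, not to the one immediately before the reduction. In history D both zero-dose periods would count under the loose use, and the first is still at Day 20. The harmless reading needs an adjacency condition that the text does not contain, and with that condition the branch is redundant.

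It is also fair to say that the consequence is small and that Section 10 leaves derivation rules to separate documents. Those documents are not at hand and may settle the matter, but the SAP sentence they would implement is still inconsistent.

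A reader might infer more than the SAP supports:

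- **That lenvatinib reductions in general will be reported too early.** Only subjects with a same-dose interruption before their first reduction could be affected, and only if the clause is programmed literally.
- **That the earlier interruption is unrelated to the reduction.** The SAP is silent on any link.
- **That a particular share of subjects, or the median, is distorted by a stated amount.** The SAP gives nothing from which to derive either.

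**Conclusion.** The second branch is inconsistent with the definitions in its own section. Read as written, it dates the first reduction at an earlier same-dose interruption, however long before and whether or not the two are related. If it is programmed literally, the affected subjects' values move earlier, by 21 to 90 days in the hypothetical histories above. If only the direct sequence was meant, the branch is redundant and nothing shifts.

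The size rests on assumed dosing days, and the number of subjects affected cannot be derived from the SAP. The effect is confined to one descriptive lenvatinib exposure summary. Counts of reductions, dose intensity, efficacy results and all tests are unaffected. This is a minor point, worth correcting because the correction is simple.

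**What to change.** Either delete the second branch, so that time to first dose reduction always runs to the date of the first reduction under the SAP's existing dating rule, or limit it to the zero-dose period that leads directly into the first lower dose. Both give the own-date values in the table above. If the time to the first hold is of interest, report time to first interruption as a separate, labelled variable.

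The cost is one sentence in the SAP and one derivation line in the dataset specification. It changes how an event is dated for reporting and implies nothing about dosing.

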#### 6.6.2 Adverse Events

Adverse events will be graded according to the National Cancer Institute [Common Terminology Criteria for Adverse Events \(NCI-CTCAE\)](#), Version 5.0. The AE verbatim descriptions (investigator terms from the CRF) will be classified into standardized medical terminology using the MedDRA Version 25.0. Adverse events will be coded to the MedDRA lower level term (LLT) closest to the verbatim term. The linked MedDRA PT and primary SOC are also captured in the database.

A TEAE is defined as an AE that emerges during treatment (and within 30 days of the last study treatment), having been absent at pretreatment (Baseline) or

- Re-emerges during treatment, having been present at pretreatment (Baseline) but stopped before treatment,  
or  
Worsens in severity during treatment relative to the pretreatment state when the AE is continuous.

Only those AEs that are treatment-emergent will be included in summary tables by treatment group. Exposure-adjusted analyses will be presented for selected AE summaries. For subjects in Arm B who received optional lenvatinib only or lenvatinib plus chemotherapy, adverse events occurring on or after the date of the crossover will be summarized separately by PT in order of decreasing frequency. All AEs, treatment-emergent or otherwise, will be presented in subject data listings.

#### 6.6.2.1 Overview of TEAEs

An overview of TEAEs reported through the study will be provided for each treatment arm. Overall summary of TEAE will include:

- the number and percentage of subjects with TEAEs
- Treatment-emergent SAEs,
- Treatment-related TEAEs,
- TEAEs of Grade 3 or higher
- TEAEs leading to treatment discontinuation (discontinuation in each study arm and discontinuation of all 3 study drugs individually in each treatment arm)
- TEAEs leading to dose reductions
- TEAEs leading to dose interruptions
- TEAEs with fatal outcomes

#### 6.6.2.2 All TEAEs

The following summaries will be provided for all TEAEs:

- TEAEs by SOC and PT
- TEAEs by decreasing frequency of PT
- Most common (eg,  $\geq 10\%$ ) TEAEs by SOC and PT
- TEAEs by SOC, PT, and worst toxicity grade

#### 6.6.2.3 Treatment-related TEAEs

The following treatment-related TEAEs will be summarized:

- Treatment-related TEAEs by decreasing frequency of PT
- Most common (eg,  $\geq 10\%$ ) treatment-related TEAEs by SOC and PT
- Treatment-related TEAEs by SOC, PT and worst toxicity grade

#### 6.6.2.4 Treatment-emergent SAEs

The incidence of treatment-emergent SAEs will be summarized as below:

- Treatment-emergent SAEs by SOC and PT
- Treatment-related treatment-emergent SAEs by SOC and PT
- Treatment-emergent SAEs by decreasing frequency of PT
- Most common (eg,  $\geq 5\%$ ) treatment-emergent SAEs by SOC and PT

In addition, a listing of serious AEs will be provided.

#### 6.6.2.5 TEAEs Leading to Treatment Discontinuation

The TEAEs leading to treatment discontinuation (discontinuation in each study arm and discontinuation of all 3 study drugs individually in each treatment arm) will be summarized by SOC and PT.

A listing of TEAEs leading to any study drug discontinuation will be provided.

#### 6.6.2.6 TEAEs Leading to Dose Reductions and Dose Interruptions

The TEAEs leading to dose reductions and dose interruptions will be summarized by SOC and PT for each treatment arm. The TEAEs leading to dose reductions and dose interruptions will be summarized for each individual drug and overall.

A listing of TEAEs leading to dose reductions and/or dose interruptions of any study drug will be provided.

#### 6.6.2.7 Grade 3 or Higher TEAEs

The following Grade 3 or higher TEAEs will be summarized:

- Grade 3 or higher TEAEs by SOC and PT
- Most common (eg,  $\geq 5\%$ ) Grade 3 or higher TEAEs by SOC and PT

In addition, a listing of Grade 3 or higher AEs will be provided.

#### 6.6.2.8 TEAEs with Fatal Outcome

The TEAEs with fatal outcome will be summarized by SOC and PT for each treatment arm. Treatment-related TEAEs with fatal outcome will also be summarized.

A listing of AEs with fatal outcome will be provided.

#### 6.6.2.9 Deaths

The number of subjects who died during the study will be summarized.

A listing of subjects who died during the study will be provided.

#### 6.6.2.10 Adverse Events of Clinical Interest

Clinically significant adverse events (CSAEs) for lenvatinib have been identified based on a thorough review of safety data from existing clinical and pharmacovigilance databases.

Evaluations of CSAEs are based on standardized MedDRA queries (SMQs), customized MedDRA queries (CMQ), or sponsor-generated queries (SGQs), which include sponsor-specified PT either alone or in addition to those listed for an SMQ or CMQ.

CSAEs will be summarized by CTCAE grade.

The subjects with CSAEs leading to dose reductions, dose interruptions, and treatment discontinuations will also be provided.

### 6.6.3 Laboratory Values

Laboratory results will be summarized using Système International (SI) units. Laboratory values that are non-missing and reported as ‘below the detectable limit’ of an assay will be replaced by half the detectable limit in the summary tables.

On-treatment laboratory tests will be defined as the laboratory tests conducted from the start of treatment to no more than 30 days after the last dose of study treatment.

#### 6.6.3.1 Hematology and Clinical Chemistry

Laboratory parameters will be graded based on CTCAE Version 5.0. In the summary of laboratory parameters by CTCAE grade, for parameters with CTCAE grading in both high and low directions (eg, calcium, glucose, magnesium, potassium, sodium), CTCAE grades in both high and low directions will be summarized separately.

The evaluation of clinical laboratory tests will focus on the following selected laboratory analytes:

##### Hematology Panel:

- hematocrit, hemoglobin, red blood cell (RBC) count, white blood cell (WBC) count, absolute neutrophil count, absolute lymphocyte count, platelet count.

##### Chemistry Panel:

- Electrolytes: bicarbonate, calcium, chloride, magnesium, phosphate, potassium, sodium
- Liver function tests: alanine aminotransferase (ALT), alkaline phosphatase, aspartate aminotransferase (AST), direct bilirubin, total bilirubin
- Renal function tests: blood urea/blood urea nitrogen (BUN), creatinine
- Thyroid function tests: thyroid stimulating hormone (TSH), free T4 level
- Other: albumin, glucose, lactate dehydrogenase (LDH), amylase, lipase, total protein

Descriptive statistics for values and changes from baseline at each scheduled visit for hematology and chemistry laboratory parameters will be provided.

In addition, the worst CTCAE grade during the treatment will be summarized by treatment arm and CTCAE grade for hematology and chemistry parameters. Shift tables from baseline to the worst CTCAE grade during treatment will be generated.

### 6.6.3.2 Thyroid-Stimulating Hormone

Thyroid-stimulating hormone values will be summarized by category according to standardized reference ranges.

### 6.6.3.3 Urinalysis

The shift of worst postbaseline proteinuria from baseline will be summarized. All urinalysis parameters (RBCs/high-power-field [HPF], blood, and protein [dipstick], and 24-hour urine protein) will be presented in by-subject listings.

### 6.6.4 Vital Signs

Descriptive statistics for vital sign parameters (systolic blood pressure (SBP) and diastolic blood pressure (DBP), pulse, respiratory rate, temperature, height and weight) and changes from baseline at each scheduled visit will be presented.

Shifts from baseline will be presented overall and by subgroups of subjects  $<18$  and  $\geq 18$ . In addition, percentiles for values of height and blood pressure (only for subjects  $<18$  years old [see Protocol Appendices 5 and 6]) will be summarized as a shift from baseline to end of treatment by category for height: 5th, 10th, 25th, 50th, 75th, 90th and 95th percentiles; and as a shift from baseline to worst (of SBP or DBP) postbaseline measurement by category:  $<90$ th, 90th to 95th, 95th to  $\leq 99$ th, and  $>99$ th percentiles.

### 6.6.5 Other Safety Analyses

#### 6.6.5.1 Electrocardiograms

Descriptive statistics for ECG parameters (HR, PR, QRS, QT, QTcB, QTcF and RR) and changes from baseline at each scheduled visit will be presented.

Shift tables of worst postbaseline values from baseline will be presented for ECG findings (categorized as normal; abnormal, not clinically significant; and abnormal, clinically significant).

Clinically abnormal ECG results in QTc (QTc Fridericia and QTc Bazett) will be categorized using the following analyses.

Absolute QTc interval prolongation will be summarized for the number (percentage) of subjects with at least 1 postbaseline ECG result during treatment:

- QTc interval  $\leq 450$  msec
- QTc interval  $>450 - 480$  msec
- QTc interval  $>480 - 500$  msec
- QTc interval  $>500$  msec

Change from baseline in QTc interval will be summarized for the number (percentage) of subjects with at least one Baseline and postbaseline ECG result during treatment:

- QTc interval increases from baseline  $>0 - 30$  msec
- QTc interval increases from baseline  $>30 - 60$  msec
- QTc interval increases from baseline  $>60$  msec

Subject listings will also be provided.

#### 6.6.5.2 Left Ventricular Ejection Fraction

The LVEF (%) assessed on echocardiogram or multiple gated acquisition (MUGA) scans will be summarized. The lowest postbaseline value and the change from baseline will be summarized descriptively.

Categorical summaries will also be presented as follows:

- Percentage reduction from baseline ( $> 0$  to  $\leq 10\%$ ,  $>10$  to  $\leq 15\%$ ,  $>15\%$ )
- Occurrence of subjects having a lowest postbaseline value of  $<50\%$ .

A subject data listing will be provided.

#### 6.6.5.3 Lansky Play Scores or Karnofsky Performance Status Scores

Lansky play scores or KPS scores will be presented as a figure showing results over time. A subject listing of Lansky play scores or KPS scores will be provided.

#### 6.6.5.4 Proximal Tibial Growth Plates

Radiographic findings of proximal tibial growth plates will be summarized at baseline and end of treatment.

A subject listing will be provided.

#### 6.6.5.5 Tanner Stage

Tanner Stage will be summarized across time by visit, and as a shift from baseline to end of treatment.

A subject listing will be provided.

#### 6.6.5.6 Dental Examination

Tooth formation abnormalities will be summarized and listed.

#### 6.6.5.7 New Anticancer Therapies During Follow-up Period

The new anticancer medications and procedures during Follow-up Period will be reported and listed.

### 6.7 Other Analyses

#### 6.7.1 Palatability

Each question in the Palatability and Acceptability Questionnaire will be summarized and listed.

#### 6.7.2 Health-Related Quality of Life

Health-related quality of life will be collected at baseline (Day -1 or at Cycle 1 Day 1 prior to treatment) and C2D1, C3D1, Week 18, C8D1, C18 D1 and at the Off-Treatment Visit. Score change from baseline in PedsQL at each analysis timepoint will be analyzed. The primary timepoint for assessment is at Week 18 for all PedsQL endpoints.

Descriptive statistics will be presented for all PedsQL endpoints at each analysis time period by treatment arm. Baseline is defined as the later value of Day -1 or at Cycle 1 Day 1 prior to treatment.

A detailed HRQoL analysis plan will be provided in a separate document and the results will be provided in a stand-alone report.

### 6.8 Exploratory Analyses

Other exploratory analyses may be conducted as appropriate.

## 7 INTERIM ANALYSES

No interim analysis is planned for this study.

## 8 CHANGES IN THE PLANNED ANALYSES

Based on the blinded review of the data, the number of subjects in the level of the stratum “time to first relapse/refractory disease  $\geq$  18 months” is only about 11 subjects out of the ITT total size of 81 subjects. To ensure a sufficient number of participants in each stratum within each treatment arm, “time to first relapse/refractory disease” stratification factor was removed from the analyses. Only the stratification factor “age at randomization” will be included in any stratified analyses.

For DCR, the SD minimum duration period is changed from 7 weeks to 5 weeks after randomization. The change was made due to the tumor assessment schedule of every 6 weeks until Week 18.

## 9 DEFINITIONS AND CONVENTIONS FOR DATA HANDLING

### 9.1 Visit Windows

Visit windows will be defined to be within upper and lower bounds of 3 days of the scheduled visit, according to the protocol, which states that efforts should be made to conduct study visits (and safety assessments) on the day scheduled ( $\pm 1$  day for Cycle 1 and within 3 days for Cycle 2 onward).

Tumor assessments should be performed at screening and every  $6\pm 1$  weeks after the date of randomization or sooner if clinically indicated until Week  $18\pm 1$  week. Then every  $9\pm 1$  weeks until Week  $54\pm 1$  week, and thereafter, every  $12\pm 2$  weeks until documentation of PD. If a subject discontinues from study treatment without disease progression, tumor assessments should continue to be performed using this schedule.

In the calculation of descriptive statistics for laboratory values and vital signs, if a visit has multiple observations, the observation closest in date and time to the target visit day will be used in the analysis. If two or more observations have the same distance to the target visit day, the one that has the highest CTCAE grade or is furthest away from the normal range will be used. The purpose of this windowing is to provide a single record per subject per visit for the calculation of descriptive statistics per scheduled visit and change from baseline per visit.

Other safety analyses (eg, worst grade laboratory results and shift tables) will include all postbaseline assessments, including scheduled and unscheduled visits.

### 9.2 Baseline Definitions

For safety assessments, the baseline value is defined as the last non-missing measurement taken on or prior to the first dose date. The first dose date is defined as the earliest date of non-zero dose administration of any study drug (ie, lenvatinib, ifosfamide, or etoposide).

Study day is defined as date of assessment – first dosing date + 1 for any assessment done on or after first dosing date; otherwise, study day is defined as date of assessment – first dosing date.

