##### 4.2.1.2 Baseline Period

The purpose of the Baseline Period is to confirm protocol eligibility as specified in the inclusion/exclusion criteria (as detailed in Section 9.3.1 and Section 9.3.2 of the Protocol). Results of baseline assessments must be obtained prior to the first dose of study drug (Cycle 1 Day 1). Baseline assessments may be performed on Day -1 or on Cycle 1 Day 1 prior to dosing. Clinical laboratory tests (Table 4 of the Protocol), including a pregnancy test (where applicable), should be performed within 72 hours prior to the first dose of study drug.

Subjects who complete the Baseline Period and continue to meet the criteria for inclusion/exclusion (as detailed in Section 9.3.1 and Section 9.3.2 of the Protocol) will begin the Randomization Phase of this study.

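### The safety baseline is set by calendar date with no pre-dose condition, so a reading taken after dosing on Cycle 1 Day 1 can be selected as baseline

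*SAP*

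**What the plan says.** Section 9.2 of the SAP sets one baseline rule for all safety assessments: "the baseline value is defined as the last non-missing measurement taken on or prior to the first dose date". It then fixes the reference point as a calendar date: "The first dose date is defined as the earliest date of non-zero dose administration of any study drug". No clock time, and no requirement that the reading precede the dose, appears in either sentence.

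Three other places bear on the same day:

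- Section 4.2.1.2 (Baseline Period): "Baseline assessments may be performed on Day -1 or on Cycle 1 Day 1 prior to dosing". It also requires baseline results to be available before the first dose, and says of the clinical laboratory tests that they "should be performed within 72 hours prior to the first dose of study drug".
- Section 6.6.3 (Laboratory Values): "On-treatment laboratory tests will be defined as the laboratory tests conducted from the start of treatment", running to 30 days after the last dose.
- Section 6.7.2 (HRQoL), for a different type of data: "Baseline is defined as the later value of Day -1 or at Cycle 1 Day 1 prior to treatment".

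**The concern.** The words for 'last' and 'on' in Section 9.2 act together. When a parameter has both a pre-dose and a post-dose record on the first dose date, both qualify and the later one is taken. The selected baseline is then a value measured under treatment.

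The safety baseline feeds:

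- the laboratory changes and the shifts to worst CTCAE grade (6.6.3.1);
- the vital-sign changes and the height and blood-pressure percentile shifts (6.6.4);
- the QTc change categories and ECG shifts (6.6.5.1);
- the LVEF change (6.6.5.2).

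Section 9.1 admits unscheduled as well as scheduled readings to the worst-value and shift analyses, but only if they are postbaseline. An unscheduled ECG or blood pressure taken on Day 1 because of an acute reaction could therefore be relabelled as baseline and might not count as a postbaseline value. Comparing safety and tolerability between the arms is a secondary objective (4.1.2), so these tables should rest on a pre-treatment reference.

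**Working it through.** The SAP states no figure on this point, so there is none to reproduce. The check applies the rule to a set of records and then compares the sections.

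**Step 1. Apply the rule.** Take one subject and one parameter with four records (assumed, for illustration):

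| Record | Date relative to first dose date | Time relative to first dose |
|---|---|---|
| Day -1 | 1 day before | 1,440 min before |
| Cycle 1 Day 1, pre-dose | same date | 60 min before |
| Cycle 1 Day 1, post-dose | same date | 240 min after |
| Day 2 | 1 day after | 1,440 min after |

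- Section 9.2 as written (latest record dated on or before the first dose date) selects the Cycle 1 Day 1 post-dose record.
- A pre-dose rule (latest record timed before the first dose) selects the Cycle 1 Day 1 pre-dose record.
- With the post-dose record removed, both rules select the pre-dose record.

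The wording therefore matters only when a same-day post-dose record exists.

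**Step 2. Effect on a change score.** Let P be the pre-dose value, D the post-dose Day 1 value and W the later value being compared.

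- Change from the pre-dose baseline: W − P
- Change under Section 9.2: W − D
- Difference: (W − P) − (W − D) = D − P

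The error equals the shift between the two Day 1 readings. It understates an increase if D > P and overstates it if D < P. With purely assumed QTcF values P = 410, D = 430 and W = 472 msec, the changes are 472 − 410 = 62 msec and 472 − 430 = 42 msec. These fall in different categories of Section 6.6.5.1 (above 60, and above 30 to 60). The example shows only that a category boundary can be crossed. It does not estimate how often.

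**Step 3. Does another section resolve it?**

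- Section 4.2.1.2 says when baseline assessments are to be done. It does not say which record the analysis uses, and it does not cover an additional reading later that day.
- Study day in Section 9.2 cannot separate the two records. Any assessment on the first dosing date gets study day 1, before or after the dose.
- Section 9.1 says that for laboratory values and vital signs "the observation closest in date and time to the target visit day will be used in the analysis". This chooses one record per visit and does not redefine baseline. It does show that clock times are expected for these data, although the baseline rule does not use them.
- Section 6.6.3 opens the on-treatment laboratory window at the start of treatment. A post-dose Day 1 laboratory value is then baseline under 9.2 and on-treatment under 6.6.3.

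Nothing in the SAP settles which record to use.

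**The case against.** The strongest reply is that the planned process already yields a pre-dose baseline. Section 4.2.1.2 puts the assessments on Day -1 or before dosing on Day 1. Read with that section, the words in 9.2 can be taken as a loose way of including the planned Day 1 pre-dose assessment. Section 10 leaves derivation rules to separate specifications, where a time condition could sit. The SAP shows no post-dose Day 1 reading, and the laboratory case is the weakest, given the 72-hour pre-dose window.

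Most of this stands as a limit on size. It does not remove the fault. A specification that follows the SAP would implement the date rule, and one that adds a time condition would depart from it. Unscheduled readings need no entry in a schedule to exist.

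Two further objections are fair. The HRQoL baseline is a separate definition for a separate analysis, so its wording does not contradict 9.2; it shows only that the pre-treatment condition was written there and left out here. And TEAEs are judged against the pretreatment state (6.6.2), so the adverse-event tables do not rest on this measurement rule.

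A reader might infer that acute drug effects are in fact being subtracted out, always toward zero and more in Arm A because it adds lenvatinib. The SAP does not support this. It documents no such readings, Step 2 shows that the error can go either way, and the SAP does not say what is given before any Day 1 reading. Nor is a post-dose laboratory value certainly lost from the worst-grade summary: Section 6.6.3 keeps it on-treatment, while the postbaseline wording of 9.1 leaves the point open.

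**Conclusion.** The point holds as a defect in a stated rule. Section 9.2 permits a post-dose value on the first dose date to serve as the safety baseline, against the intent of Section 4.2.1.2, and for laboratory tests it overlaps the on-treatment window of Section 6.6.3.

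The consequence is conditional on a post-dose record existing on that date for the parameter in question. For such subjects, change-from-baseline and shift summaries are off by the difference between the two Day 1 readings, and an ECG or vital-sign reading may leave the postbaseline set. Absolute QTc categories and the count of LVEF below 50% subtract no baseline, so only that relabelling could touch them. The number of subjects affected, the direction and any difference between arms cannot be derived from the SAP. If no such records exist, no table changes. The efficacy analyses, including the primary PFS comparison, do not use this baseline. The change is worth making because it is cheap and removes an ambiguity that two programmers could resolve differently.

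**What to change.** Reword Section 9.2 along these lines:

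- The safety baseline is the last non-missing measurement before the first dose of any study drug, judged by date and time.
- Where the time is missing on the first dose date, an assessment planned as pre-dose under Section 4.2.1.2 is treated as pre-dose. Unscheduled or nominally post-dose records without a time are not eligible as baseline.
- Post-dose records on Cycle 1 Day 1 count as postbaseline, in line with the on-treatment definition in Section 6.6.3.

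The cost is about one sentence in the SAP and a matching rule in the dataset specifications. The small downside is that a few untimed, unscheduled Day 1 records can no longer serve as baseline, so an earlier value is used for those subjects. Treating planned Day 1 assessments as pre-dose keeps that loss small. Without it, untimed but properly planned Day 1 values could be discarded in favour of a screening value from as early as Day -28.
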